ALC = absolute lymphocyte count; ALT = alanine aminotransferase; ANC = absolute neutrophil count; aPTT = activated partial thromboplastin time; AST = aspartate aminotransferase; INR = international normalized ratio PT = prothrombin time; ULN = institutional upper limit of normal; WBC = white blood cell

¹ If receiving anticoagulant therapy, values should be within therapeutic range of intended use

Any Grade 3 or higher abnormality in any serum chemistry or hematology parameter should be discussed and approved by the Medical Monitor prior to enrollment (even if considered not clinically significant)

10. Women of childbearing potential (WOCBP) and fertile males with WOCBP partners must use highly effective contraception ([CTFG, 2014](#)) throughout the Treatment and Evaluation Period (from first dose and through 120 days after final dose of study drug). Contraception must include at least one barrier method to minimize risk of fluid transmission.
11. Provide written informed consent and is willing and able to comply with all study procedures.

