6.3.5.2 Pembrolizumab Dose Modification and Toxicity Management

Immune-related Adverse Events Associated with Pembrolizumab

AEs associated with pembrolizumab exposure may represent an immunologic etiology. These immune-related AEs (irAEs) may occur shortly after the first dose or several months after the last dose of pembrolizumab treatment and may affect more than one body system simultaneously. Therefore, early recognition and initiation of treatment is critical to reduce complications. Based on existing clinical trial data, most irAEs were reversible and could be managed with interruptions of pembrolizumab, administration of corticosteroids and/or other supportive care. For suspected irAEs, ensure adequate evaluation to confirm etiology or exclude other causes. Additional procedures or tests such as bronchoscopy, endoscopy, skin biopsy may be included as part of the evaluation. Based on the severity of irAEs, withhold or permanently discontinue pembrolizumab and administer corticosteroids.

Dose modification and toxicity management guidelines for irAEs associated with pembrolizumab are provided in [Table 6-4](#). The Medical Monitor will be consulted regarding continued dosing of CRS-207 should any of these events occur. During the Safety Run-in Period withholding pembrolizumab or administering systemic steroids would define an unacceptable toxicity.

Table 6-4 Dose Modification and Toxicity Management Guidelines for Immune-Related Adverse Events Associated with Pembrolizumab

General Instructions:				
Immune-related AEs	Toxicity grade or conditions (CTCAEv4.0)	Action taken to pembrolizumab	irAE management with corticosteroid and/or other therapies	Monitor and follow-up
Pneumonitis	Grade 2	Withhold	
 Administer corticosteroids (initial dose of 1-2mg/kg prednisone or equivalent) followed by taper 	
 Monitor subjects for signs and symptoms of pneumonitis Evaluate subjects with suspected pneumonitis with radiographic imaging and initiate corticosteroid treatment Add prophylactic antibiotics for opportunistic infections
	Grade 3 or 4, or recurrent grade 2	Permanently discontinue		

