6.4.2.2 Survival Follow-Up

Following the Treatment and Evaluation Period, subjects will be contacted at 12 [REDACTED] [REDACTED] to assess survival and subsequent cancer-related therapies. A telephone contact should also be scheduled at least 90 days post-treatment discontinuation to satisfy reporting requirements for SAEs and events of clinical interest.

Follow-up will continue until death of the subject, loss to follow-up, or close of study by the Sponsor. For subjects who withdraw from the study prior to completion of the Follow-up Period, reasonable efforts will be made to collect survival outcome. Sites will attempt to obtain vital

status data from public records or other external sources where possible if a subject withdraws consent from study (i.e. refuse follow-up for vital status) or is documented as lost to follow up. All deaths must be reported on the eCRF.

The Sponsor may request survival status be assessed at additional time points during the course of the study. These additional contacts may be requested for safety review, interim analysis, and/or final analysis. All subjects who are not known to have died prior to the request for these additional survival status time points will be contacted at that time.

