7.3 Serious Adverse Event Reporting – Procedures for Investigators

7.3.1 Initial Reports

SAEs will be collected from the time of first study drug administration through 90 days following cessation of treatment, or 28 days following cessation of treatment if the subject initiates new anticancer therapy, whichever is earlier. SAEs and events of clinical interest must be reported to the Sponsor (or designee) within 24 hours of the knowledge of the occurrence. Outside of the 90-day period, only SAEs considered related to the administration of study drug must be reported to the Sponsor.

In the event an SAE is observed or reported, the SAE report will be completed as thoroughly as possible including all available details about the event and the signature of the Investigator. If the Investigator does not have all information about an SAE, the Investigator will not wait to receive additional information before notifying the Sponsor of the event and completing the form. The form will be updated when additional information is received.

Complete the paper SAE form for each SAE. The SAE form will be faxed or emailed to the Sponsor or designee within 24 hours of awareness of the initial or any follow-up information, and designated study personnel will be notified electronically. If the SAE falls on a weekend or

holiday, an email notification is acceptable but must be followed by an SAE reporting form on the next business day.

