7.4 Pregnancy Reporting

If the subject or partner of a subject participating in the study becomes pregnant during the study or within 120 days of discontinuing study drug (or 28 days if the subject initiates new anticancer therapy, whichever is earlier) the Investigator should report the pregnancy within 24 hours of being notified. Designated safety personnel will then forward the Exposure In Utero form to the Investigator for completion.

A subject becoming pregnant while on study drug will immediately be withdrawn from the study and EOT study procedures will be performed.

The subject or partner should be followed by the Investigator until completion of the pregnancy. If the pregnancy ends for any reason before the anticipated date, the Investigator should notify designated safety personnel. At the completion of the pregnancy, the Investigator will document the outcome of the pregnancy. SAE reporting procedures should be followed if the outcome of the pregnancy meets the criteria for immediate classification as an SAE (i.e. postpartum complication, spontaneous abortion, stillbirth, neonatal death, or congenital anomaly).

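### Protocol 7.3.1: for subjects who start new anticancer therapy, the literal wording leaves drug-related SAEs on Days 29-90 after treatment under neither reporting sentence

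*Protocol*

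**What the plan says.** Protocol 7.3.1 makes three statements about SAEs.

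- Collection window, with its default end point: "SAEs will be collected from the time of first study drug administration through 90 days following cessation of treatment". The same sentence then sets a shorter alternative: "or 28 days following cessation of treatment if the subject initiates new anticancer therapy, whichever is earlier".
- Deadline: "SAEs and events of clinical interest must be reported to the Sponsor (or designee) within 24 hours of the knowledge of the occurrence".
- Late events: "Outside of the 90-day period, only SAEs considered related to the administration of study drug must be reported to the Sponsor".

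Other parts of the protocol bear on the same period.

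- Section 6.3.5.2 says immune-related events "may occur shortly after the first dose or several months after the last dose of pembrolizumab treatment".
- Section 6.4.2.2, repeated in a footnote to the Schedule of Events, says: "A telephone contact should also be scheduled at least 90 days post-treatment discontinuation to satisfy reporting requirements for SAEs and events of clinical interest". Neither place makes an exception for new therapy.
- Section 7.3.5 makes suspected CRS-207 or Listeria infection reportable whatever its timing, and 6.4.2.2 requires every death to be entered on the eCRF.

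For pregnancy, Section 7.4 requires a report if conception occurs during the study or "within 120 days of discontinuing study drug (or 28 days if the subject initiates new anticancer therapy, whichever is earlier"). Inclusion criterion 10 requires contraception "from first dose and through 120 days after final dose of study drug", with no new-therapy exception. Section 6.4.4.2 repeats the 120 days.

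**The concern.** The collection sentence has two end points, Day 28 and Day 90. The late-event sentence refers to only one of them. A subject who starts another anticancer therapy therefore leaves collection at Day 28 but does not come under the related-SAE duty until after Day 90. A related SAE on Day 50 is not clearly reportable, yet the same SAE on Day 100 is. The protocol gives no reason for that order, which suggests a drafting slip.

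The group is foreseeable: Protocol 6.1 already provides for subjects who start other therapy within 28 days of the last dose. The interval is also one in which the protocol itself expects that delayed immune-related harm may occur. Under 7.3.3 the sponsor's expedited-reporting clock starts when it receives information. An unexpected related SAE that no sentence obliges the site to send may never start that clock.

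**Working it through.** No sample size, power or event count is involved. The check sets the windows side by side, counting days after cessation of treatment.

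**Inputs.** Protocol 7.3.1: collection to Day 90, or to Day 28 with new therapy if earlier; related-SAE duty after Day 90. Protocol 7.4: pregnancy reporting to Day 120, or Day 28 with new therapy. Inclusion criterion 10: contraception to Day 120. SAP 5.4: on-therapy period ends 28 days after the last dose.

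**Drug-related SAE, literal reading of 7.3.1**

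| Onset | No new therapy | New therapy started |
|---|---|---|
| Up to Day 28 | collected | collected |
| Days 29-90 | collected | neither sentence |
| After Day 90 | reportable as related | reportable as related |

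- Gap without new therapy: 90 - 90 = 0 days.
- Gap with new therapy: 90 - 28 = 62 days.

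**Effect of the start date.** The text does not say what happens if new therapy begins between Day 28 and Day 90. Take a start on Day 60. If the cut-off moves back to Day 28, the gap is still 62 days and events already collected change status. If collection instead runs until the new therapy starts, the gap is 90 - 60 = 30 days. Hence up to 62 days.

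**Whether another rule fills the interval**

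- Ordinary AE recording (Protocol 6.4.3.4 and 7.1) stops at 28 days or at the start of new therapy, so it does not.
- Potential Hy's Law cases (7.1.1.2) are covered only through the EOT visit.
- Suspected CRS-207 or Listeria infection (7.3.5) and deaths (6.4.2.2) are covered.
- Part of 7.1.1.2 is redacted, so other events of clinical interest may also be covered.

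**Effect on the planned tables.** SAP 10.1 counts an AE as treatment-emergent only if onset is in the on-therapy period, and SAP Table 14.3.2.1 is restricted to serious treatment-emergent events. Days 29-90 begin after that period closes, so none of the 62 days feeds those tables. The by-subject AE listing in SAP 10.1 could change.

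**Pregnancy.** If the on-study trigger in 7.4 means on treatment only, the difference from the contraception period is 120 - 28 = 92 days. If it includes the Follow-up Period, which Protocol 6.1 makes part of the study and runs for at least 12 months from the last dose, the difference is 0 days for anyone still in follow-up.

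**The case against.** The strongest defence is that 7.3.1 was never meant to exempt these events. The 24-hour sentence has no time limit, and the paper form is to be completed for each SAE. The late-event sentence can be read as releasing sites from unrelated late SAEs while keeping related ones. The unconditional call at 90 days or later also suggests that the sponsor meant to hear about this period. On that reading the gap is 0 days.

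This stands in part: the gap is one of drafting, not a stated exclusion. It does not remove the point. The 24-hour sentence sets a deadline rather than a window, and if it covered every SAE at any time, the restriction to related events in the last sentence would have no function. Treating the 90-day period as whichever window applies is the natural intention, but it replaces the number in the text. The planned call conflicts with the 28-day cut-off and does not resolve it.

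Three stronger inferences are tempting and are not supported.

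- That pregnancies on Days 29-120 go unreported. Section 7.4 also triggers on pregnancy during the study, and 6.4.4.2 states a general duty to report, referring to 7.4. Reading that trigger to include follow-up leaves the 120- and 28-day limits with little to do, so the text is ambiguous. The 28-day cut-off is also an express rule, not a hole between sentences. The protocol's remarks on listeriosis in pregnancy concern wild-type Listeria, and 6.4.4.2 calls fetal effects unknown.
- That the trial's safety result is understated. The planned treatment-emergent tables stop at 28 days whatever 7.3.1 says, and SAP 10.1 summarises deaths overall.
- That a known number of subjects is affected. Assuming 30% to 60% of the planned 79 start new therapy within 90 days would give 24 to 47 (0.30 x 79 and 0.60 x 79). The documents give no such rate, and the result counts people to whom the wording could apply, not missed events.

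**Conclusion.** The point holds for SAE reporting. On the literal wording of Protocol 7.3.1, drug-related SAEs with onset on Days 29-90 in subjects who start new anticancer therapy are required by neither sentence. The gap is up to 62 days for each such subject and zero for others. This rests on taking the 90-day period at its stated length and the 24-hour sentence as a deadline only. It excludes suspected CRS-207 or Listeria infection, deaths, and anything covered in redacted text. What is at stake is SAE reporting, expedited reporting and the completeness of the AE listing; no efficacy figure and no planned treatment-emergent table changes.

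The pregnancy wording is a lesser, separate matter: 28 days in 7.4 against 120 days in the contraception requirement, with an undefined on-study trigger. It needs reconciling and supports no conclusion about unreported cases.

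Practical reach in this trial is limited. SAP 3.5 records that development has ceased, that every subject had completed the EOT visit by 31 January 2018, and that no further follow-up is expected.

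**What to change.** In Protocol 7.3.1, replace the opening of the late-event sentence with wording such as: after the applicable collection period (28 or 90 days). Related SAEs are then reportable at any time. State how a start of new therapy between Day 28 and Day 90 affects the window, and reconcile 7.3.1 with the 90-day contact in 6.4.2.2 and the Schedule of Events footnote.

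Reconcile 7.4 with inclusion criterion 10 and 6.4.4.2, and define what counts as during the study. Which windows should apply is for the sponsor to decide.

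The cost is a few words and perhaps a few more SAE reports, some confounded by the new therapy. No visits are added, because subjects are already contacted in follow-up. If the protocol is no longer to be amended, the study report should say how related SAEs on Days 29-90 were handled in subjects on new therapy.

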7.3.2 Safety Reporting Contact Information

Safety contact information may be found in the Study Reference Manual.

7.3.3 Expedited Reporting Requirements

The Sponsor (or designee) will report all SAEs that are unexpected and considered related to the administration of the investigational agent to the appropriate health and regulatory authorities and Investigators in the form of an expedited safety report within 15 calendar days after receiving information on the SAE. The Investigators will notify their reviewing IRB/EC and other committee(s) as required by institutional policies.

The Sponsor will also report to the appropriate health and regulatory authorities by facsimile, e-mail, or phone within 7 days of receiving the information, any unexpected life-threatening or fatal SAEs that are considered related to the investigational agent.

7.3.4 Follow-Up Reports

The Investigator must continue to follow the subject until the SAE has subsided or until the condition becomes chronic in nature, stabilizes (in the case of persistent impairment), or the subject dies.

Within 24 hours of receipt of follow-up information, the Investigator must update the SAE form and submit any supporting documentation (e.g. subject discharge summary or autopsy reports) via fax or e-mail to the Sponsor or designee.

7.3.5 Adverse Events of Special Interest

Suspected infection with CRS-207 and/or *Listeria* are considered AESIs and should be reported following SAE reporting procedures in [Section 7.3](#) irrespective of temporal relationship to study drug administration.

In the event a subject has a positive *Listeria* culture at any time during or after study participation (except within 4 days after a CRS-207 infusion), a detailed narrative of the event should be reported to the Sponsor within 24 hours of the event.

All AESIs must be reported for the duration of the study regardless of causality.

7.4 Pregnancy Reporting

If the subject or partner of a subject participating in the study becomes pregnant during the study or within 120 days of discontinuing study drug (or 28 days if the subject initiates new anticancer therapy, whichever is earlier) the Investigator should report the pregnancy within 24 hours of being notified. Designated safety personnel will then forward the Exposure In Utero form to the Investigator for completion.

A subject becoming pregnant while on study drug will immediately be withdrawn from the study and EOT study procedures will be performed.

The subject or partner should be followed by the Investigator until completion of the pregnancy. If the pregnancy ends for any reason before the anticipated date, the Investigator should notify designated safety personnel. At the completion of the pregnancy, the Investigator will document the outcome of the pregnancy. SAE reporting procedures should be followed if the outcome of the pregnancy meets the criteria for immediate classification as an SAE (i.e. postpartum complication, spontaneous abortion, stillbirth, neonatal death, or congenital anomaly).

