13. CD4 and CD8 Counts and HLA typing are performed by central laboratory. Collection is described in the Laboratory Manual. If HLA sample is rejected for analysis, an additional sample may be collected at a later time point
14. Thyroid panel should be collected during ODD NUMBERED cycles only (i.e. every 6 weeks). Blood draws may be taken up to 72 hours before each required dosing cycle. Unresolved abnormal labs considered drug related AEs should be followed until resolution. Panel not required at EOT if labs are within normal range during treatment.
15. Hematology, serum chemistry: Blood draws may be taken up to 72 hours before each dosing cycle where study drug is administered.

16. Coagulation Panel may be repeated at same frequency as hematology/serum chemistry if clinically indicated; beginning at Cycle 6 frequency may be reduced to every 12 weeks unless clinically indicated.
17. Pregnancy Test: Serum pregnancy test required at screening, and urine pregnancy tests are required before doses on Day 1 of each cycle and EOT for WOCBP.
18. Whole blood for PBMC and Serum and plasma for immune monitoring collected and processed per Laboratory Manual. Samples should be collected prior to study drug administration. Cycle 2 Day 15 collection should be taken on day of biopsy. Additional samples may be collected at Investigator's discretion.
19. Blood for CRS-207 Surveillance will be collected at EOT or 7 days after last CRS-207 dose to assess clearance of CRS-207. Obtain sample(s) prior to initiation of antibiotics (blood must additionally be collected from the central venous access device if applicable). After last dose of CRS-207, blood will continue to be collected at [REDACTED]. Collection and shipment are described in the Laboratory Manual.
20. Pembrolizumab will be administered via IV infusion for 30 minutes. Obtain vital signs (BP, pulse, respiratory rate, temperature) prior to, and immediately following each pembrolizumab infusion. Pembrolizumab may be administered up to 3 days before or after the scheduled Day 1 of each cycle due to administrative reasons. If subjects on same-day dosing schedule experience severe infusion-related reactions related to the pembrolizumab infusion, the CRS-207 infusion may be delayed to Day 2.

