Blood will be collected at EOT to assess clearance of CRS-207 and at [REDACTED]. The EOT Visit will occur no more than 28 days after the last dose of study drug. If the subject has discontinued CRS-207 but continues on pembrolizumab, the subject will be asked to come back to the clinic [REDACTED]

[figure not shown]
[REDACTED] If the subject begins another anticancer therapy before the end of the 28-day period, all EOT Visit assessments should be completed prior to commencing the new therapy. Unresolved AEs will be monitored until resolution or confirmed stability of the event. Subjects that discontinue all study drugs and complete the EOT without documented progressive disease (based on RECIST v1.1) will be asked to complete Evaluation Visits for tumor imaging every 6 weeks until documented disease progression or start of another anticancer therapy. [REDACTED]

At the end of the Treatment and Evaluation Period subjects will enter the Follow-up Period of the study and will be followed for survival, subsequent cancer-related therapies, and post treatment monitoring for CRS-207 [REDACTED] until death or close of study by the Sponsor. The Sponsor may request survival status be assessed at additional time points during the course of the study. Sites will attempt to obtain vital status data from public records or other external sources where possible if a subject withdraws consent from study (i.e. refuse follow-up for vital status) or is documented as lost to follow up. Follow-up will continue for at least 12 months from last dose of study drug.

Figure 6-1 ADU-CL-14 STUDY DESIGN

Advanced Gastric/GEJ/Esophageal Adenocarcinoma, N = 79

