6.2.4 Subject Discontinuation

Subjects will be encouraged to complete the study; however, they may voluntarily withdraw from treatment or the study at any time. The Investigator will provide a written explanation describing the reason for discontinuation from treatment or study in a source document, which will be entered into the electronic case report form (eCRF). Subjects who discontinue treatment

will complete the EOT assessments, [REDACTED] and post-treatment monitoring for CRS-207. Subjects will be encouraged to participate in the Follow-up Period. In the case of subjects lost to follow-up, attempts to contact the subject must be made and documented in the subject's study records. Sites will attempt to obtain vital status data from public records or other external sources where possible if a subject withdraws consent from study (i.e. refuse follow-up for vital status) or is lost to follow up.

A subject in this clinical study may be discontinued from treatment for any of the following reasons:

- The subject withdraws consent or requests discontinuation for any reason
- Occurrence of any medical condition or circumstance that exposes the subject to substantial risk and/or does not allow the subject to adhere to the requirements of the protocol
- Any serious adverse event (SAE), clinically significant AE, severe laboratory abnormality, intercurrent illness, or other medical condition which indicates to the Investigator that continued participation is not in the best interest of the subject
- Pregnancy
- Subject failure to comply with protocol requirements or study-related procedures
- Termination of the study by the Sponsor or the regulatory authority

Subjects who experience an unacceptable toxicity directly attributable to either pembrolizumab or CRS-207 may continue on study and receive either pembrolizumab or CRS-207 as single agent treatment following completion of the Sponsor Consultation Form and approval by the Medical Monitor. Alternatively, study drug administration may revert back to consecutive day-dosing regimen as performed in Cycle 1.

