6.3.8 Prohibited Medications and Procedures

A subject may be removed from the study for use of prohibited medications or procedures. Approval must be obtained from the Medical Monitor for a subject to continue dosing if a prohibited medication is administered within the specified timeframes. The following therapies are not permitted or restricted during the study:

- Non-study chemotherapy or immunotherapy (approved or investigational)
- TNF pathway inhibitors or PI3 kinase inhibitors
- Palliative radiation
- Live vaccines (examples of live vaccines include, but are not limited to: measles, mumps, rubella, chicken pox, yellow fever, rabies, BCG, and typhoid [oral] vaccine). Seasonal influenza vaccines for injection are generally killed virus vaccines and are allowed. However, intranasal influenza vaccines (e.g. Flu-Mist[®]) are live attenuated vaccines, and are not allowed.
- Any major surgery or surgical procedure; if required must be discussed with the Medical Monitor to determine if it is appropriate for the subject to continue study treatment
- Any other investigational product

If a subject requires an emergent implant of a prohibited device while on therapy, the subject will receive a 14-day IV antibiotic regimen ([Section 6.3.6.1](#)).

In addition, the following medications are only restricted prior to and after CRS-207 infusions as indicated:

- Systemically active steroids for more than 3 days or use of any systemic steroids within 14 days before or after CRS-207 infusion, with the exception of inhaled and topical steroids
- Filgrastim (granulocyte colony stimulating factor; G-CSF) or sargramostim (granulocyte-macrophage colony stimulating factor; GM-CSF) within 14 days prior to or 14 days after CRS-207 infusion
- Prophylactic vaccines (e.g. pneumococcal vaccine, influenza vaccine) within 14 days prior to or after CRS-207 infusion

The following therapies should not be administered during the study unless medically necessary; approval must be obtained from the Medical Monitor for a subject to continue dosing if therapy is given concurrently with study participation:

- General anesthesia or deep sedation
- Aspirin >325 mg/day
- Acetaminophen > 4 g/day
- Systemic antibiotics

There are no prohibited therapies during the Follow-up Period.

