6.4 Study Assessments and Procedures

Screening assessments will be conducted to confirm eligibility and to obtain baseline measurements; screening must be completed within 28 days prior to first dose of study drug. An

enrollment form will confirm subject eligibility after completion of all screening procedures. Subjects must initiate dosing of study drugs within 2 weeks of completed enrollment.

Subjects will be requested to complete multiple clinic visits during the initial four dosing cycles; visit frequency is reduced beginning at Cycle 4 and beyond. An EOT Visit will occur within 28 days after the last dose of study drug. If the subject begins another anticancer therapy before the end of the 28-day period, all EOT Visit assessments should be completed prior to commencing the new therapy. Unresolved AEs will be monitored until resolution or confirmed stability of the event.

After the EOT Visit, subjects will be followed [REDACTED] to collect data on survival, CRS-207 monitoring, and any subsequent cancer-related therapies until death or close of study by the Sponsor. Sites will attempt to obtain vital status data from public records or other external sources where possible if a subject withdraws consent from study (i.e. refuse follow-up for vital status) or is documented as lost to follow up. Follow-up will continue for at least 12 months from last dose of study drug.

All study visits (and visit windows), assessments, and procedures will be performed as indicated in the Schedule of Events ([Table 1-1](#) or [Table 1-2](#)). Further details of study procedures and assessments can be found in the Study Reference and Laboratory Manuals.

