6.4.4.4 Blood Cultures for CRS-207 Surveillance

Blood samples will be obtained from subject's peripheral vein at the EOT visit or 7 days after the last dose of CRS-207 (for patients continuing on pembrolizumab) (prior to initiation of antibiotics) to monitor for presence of CRS-207. For subjects with a central venous access device, a blood sample will also be taken through the port at time points indicated for CRS-207 testing. Subjects with samples positive for the presence of CRS-207 [REDACTED] [REDACTED] and be re-tested until negative cultures are confirmed.

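### Section 7.4 takes a pregnant subject off the study where Section 6.2.4 only stops treatment, so read literally the post-EOT CRS-207 cultures and the 90-day safety call could lapse; Section 6.3.8 carries a weaker form of the same risk

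*Protocol*

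**What the plan says.** Protocol Section 7.4 gives the rule for a pregnancy on study drug: "A subject becoming pregnant while on study drug will immediately be withdrawn from the study and EOT study procedures will be performed". After that it provides only for following the pregnancy to its outcome. It does not mention CRS-207 cultures.

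Section 6.2.4 treats the same event differently. Pregnancy is an item under the sentence "A subject in this clinical study may be discontinued from treatment for any of the following reasons". The section has subjects who stop treatment complete the EOT assessments, a redacted item "and post-treatment monitoring for CRS-207. Subjects will be encouraged to participate in the Follow-up Period".

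Section 6.3.8 deals with prohibited therapy: "A subject may be removed from the study for use of prohibited medications or procedures". Its next sentence requires Medical Monitor approval for dosing to continue.

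The CRS-207 surveillance after EOT is described in several places:

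- Section 6.1: subjects entering the Follow-up Period "will be followed for survival, subsequent cancer-related therapies, and post treatment monitoring for CRS-207".
- Section 6.4: after the EOT Visit subjects are followed "to collect data on survival, CRS-207 monitoring, and any subsequent cancer-related therapies until death or close of study by the Sponsor".
- Footnote 19 to the schedules of events in the Synopsis: "After last dose of CRS-207, blood will continue to be collected at" times that are blacked out.
- Section 6.4.4.4: a subject with a positive sample is to undergo a redacted step "and be re-tested until negative cultures are confirmed".

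Section 6.4.2.2, on survival follow-up, also schedules a telephone contact at least 90 days after treatment stops, to meet the reporting requirements for serious adverse events and events of clinical interest.

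**The concern.** CRS-207 is a live attenuated *Listeria* strain, and the protocol plans blood cultures after treatment to check that it has cleared. Sections 6.1 and 6.4 place the later cultures in the follow-up that comes after EOT. A site that obeys Section 7.4 to the letter would close the subject's study participation at EOT. It could then reasonably conclude that neither the later cultures nor the 90-day call is due.

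Section 6.3.4.1 names pregnant women and immunocompromised people as the groups chiefly affected by wild-type listeriosis. Section 7.4 concerns the first group. Section 6.3.8 can reach the second, since TNF pathway inhibitors are on its list. The wording thus permits scheduled surveillance to stop in subjects for whom one would most want it to go on. A duty to report an infection would remain, but the planned test that might find one could be gone.

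**Working it through.** No arithmetic applies. The check is whether the sections conflict and, if so, what is exposed.

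1. **Are leaving treatment and leaving the study different in this protocol?** Yes. Section 6.2.4 lets subjects withdraw from one or the other and records the reason for each. Section 6.5.3 and SAP Section 6.2 report reasons for treatment and study discontinuation separately. A site must choose between them.

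2. **Do 7.4 and 6.2.4 agree on pregnancy?** No. Section 7.4 is mandatory and acts on the study; Section 6.2.4 is permissive and acts on treatment. Neither refers to the other. Section 7.4 shows no redaction in the public text, so no hidden wording there settles it.

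3. **Does leaving the study end follow-up?** The protocol's own usage suggests so. Section 6.4.2.2 speaks of subjects who withdraw from the study before the Follow-up Period is complete. The fallback it offers them is an effort to obtain survival status. It offers none for cultures.

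4. **What survives under 7.4?** The EOT procedures, which the section requires. By footnote 19 and Sections 6.3.6 and 6.4.4.4, these bring the CRS-207 culture, drawn before antibiotics, and the antibiotic course meant to clear residual organism (where these were not already done 7 days after the last CRS-207 dose). Pregnancy follow-up survives too, as does reporting of serious adverse events (Section 7.3.1) and of *Listeria* infection (Sections 6.3.6.1, 6.4.4.4.1 and 7.3.5).

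5. **What is exposed on a literal reading?** The scheduled cultures after EOT, including re-testing after a positive result, and the 90-day contact. Scheduled survival contacts are exposed as well, but Section 6.4.2.2 backs these up through reasonable efforts, public records and contacts requested by the Sponsor.

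6. **Does 6.3.8 raise the same issue?** In weaker form. Removal acts on the study, as in 7.4, but is optional. Section 6.2.4 covers prohibited therapy only by inference, through its item on failure to comply with the protocol.

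7. **Size.** The documents give no rate of pregnancy or of prohibited-therapy use, and the times of the post-EOT cultures are redacted. No figure can be put on the loss.

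**The case against.** The strongest reply is that Section 6.2.4 already settles the matter. A subject withdrawn for pregnancy has also stopped treatment, and subjects who stop treatment are to complete post-treatment CRS-207 monitoring; only the Follow-up Period is merely encouraged. Other duties are tied to dosing rather than study status: footnote 19 runs from the last CRS-207 dose, the 90-day call from treatment discontinuation, and re-testing after a positive culture carries no visible exception. This stands as a fair reading and is why the loss is only possible. It does not remove the defect, because Section 7.4 is the specific rule on pregnancy and points a site the other way.

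It is also said that the main safeguards remain: the EOT culture, the antibiotics, pregnancy follow-up and *Listeria* reporting. That is correct and narrows the exposure to what comes after EOT. But *Listeria* reporting is triggered by a suspected infection or a positive culture; it does not schedule the culture. For subjects on immunosuppressants, Section 6.3.8 strongly recommends prophylactic antibiotics on or after study, which mitigates the risk but is only a recommendation.

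A reader might infer that a pregnant subject would leave with no check for CRS-207 at all, that 6.3.8 obliges sites to remove subjects, or that CRS-207 has been shown to be dangerous in these groups. The documents support none of these. EOT procedures are kept, 6.3.8 is discretionary, and the risk-group sentence in Section 6.3.4.1 concerns wild-type *Listeria*; the same section describes CRS-207 as more than 1000 times less toxic in mice.

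**Conclusion.** The conflict between Sections 7.4 and 6.2.4 is real, and it lies in operative text that a site would follow. Its consequence is limited: on a literal reading, the post-EOT CRS-207 cultures and the 90-day safety contact could stop. Section 6.3.8 adds a weaker version of the same risk. The point is minor, with medium confidence.

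This rests on two assumptions: that a site would take study withdrawal to end follow-up, as Section 6.4.2.2 implies, and that the redacted text, including the gap inside the key sentence of Section 6.2.4, does not say otherwise. Few subjects are likely to be affected.

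A reader might go further and suppose that survival or response results are biased. They are not touched: SAP Section 7 lists efficacy endpoints without summarizing them. SAP Section 3.5 records that every subject had completed the EOT visit by 31 January 2018 and that no more follow-up was expected. The value of the point is in the protocol wording, not in any result of this trial.

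**What to change.** In Section 7.4, replace *withdrawn from the study* with *discontinued from study treatment*. In Section 6.3.8, replace *removed from the study* with *discontinued from study treatment*. In both add: *EOT procedures, post-treatment CRS-207 monitoring, the 90-day safety contact and survival follow-up continue per Section 6.2.4 unless consent is withdrawn.*

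The sentence names the 90-day contact because Section 6.2.4 does not. It leaves out tumor imaging on purpose, since the point concerns safety surveillance and rests on no lost scan. The requirement in 6.3.8 for Medical Monitor approval of continued dosing stays as it is.

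The cost is one phrase and one sentence in each of two sections, with no new visit type. The small downside is that already scheduled contacts and cultures continue in a few subjects.
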